## Inclusion of Women, Minorities and Children

**Inclusion of women:** Women will be included in this study. There are sex differences in the DA-releasing effects of AMPH, that might impact the effects of AMPH on a number of behavioral measures that are relevant to this application. Thus, while no sexual dimorphism has been reported in the therapeutic effects of TCT, and none were noted in our study of AMPH effects on APS learning, we will strive to include enough men and women in the study to conduct meaningful analyses of sex effects on both AMPH sensitivity and biomarker predictors of AMPH effects on APS learning. To control for potential effects of menstrual cyclicity on biomarkers or drug sensitivity, Aim 1 drug testing will begin within days 1 - 7 of menses onset (our standard protocol for over a decade e.g. 106). There is a strong rationale for assessing the predicted drug effects in both men and women, because these findings will have implications in terms of the potential clinical applications of this PACT design.

[figure not shown]
Several steps will be taken to avoid exposure of any fetus to amphetamine. First, females who are pregnant, nursing, imminently planning pregnancy or have a positive urine pregnancy test on screen day or any test day will be excluded from this study. Second, female subjects of childbearing potential (defined here as any female who has not had a total hysterectomy and/or bilateral oophorectomy, or who has had a menstrual cycle within the past year) will have urine pregnancy tests weekly through the 10th week of TCT ("Surecheck Early Pregnancy Test"). Second, in all subjects of childbearing potential, Aim 1 testing will begin within days 1 - 7 of menses onset. Third, to participate in this study, females of childbearing potential must agree to use a double-barrier method of contraception when participating in sexual intercourse (regardless of other methods of contraception). If a female of childbearing potential becomes pregnant during the study, the subject will be exited from the study. The investigator will determine whether the subject was exposed to active study drug or placebo, and notify the subject of this information.

**Inclusion of minorities:** Ethnic representation is based on recruitment response, with every effort made to include minority groups. Exclusion criteria are not based on ethnicity. Minority participation should thus reflect the ethnic make-up of the San Diego community. Based on our experience, the following ethnic percentages are expected in the study sample, based on the past 4 years of subject recruitment: White, not of Hispanic origin = 54%; Hispanic = 9.5%; Black, not of Hispanic origin = 3.2%; Asian = 32%; American Indian or Alaskan native = 0%. The source of recruitment information is recorded for each subject (e.g. website, fliers, newspaper advertisements, etc.), providing us with ethnic "success rates" for particular means of recruitment. Ethnic representation is then reviewed with annual progress reports. Recruitment efforts are adjusted, based on "success rates" of specific recruitment means, to respond to any significant deviation from the projected ethnic recruitment rates. The UCSD Medical Center is an equal opportunity employer; pursuant to state legislation, the University of California no longer applies affirmative action criteria in the student application process.

**Inclusion of Children:** Children younger than 18 are not included because of the diagnostic complexities and clinical heterogeneity introduced by studying psychosis in that population, as well as the ethical considerations involved in the administration of psychoactive drugs to children. The primary therapeutic intervention (TCT) has not been thoroughly studied in psychosis spectrum patients younger than 18 years of age; one small report was "negative" but likely under-powered; one larger report detected positive effects. Because the key question in the present R33 application will be confounded by a lack of therapeutic response to the TCT intervention, it was felt that inclusion of this younger cohort should await more definitive evidence for such an effect. In addition, several key "biomarker" measures are either highly variable and not fully developed or not established in younger children.

## Recruitment and Retention Plan

We anticipate that over the course of this study we will consent 69 SZ individuals for screening, from whom we will advance 54 individuals to in-laboratory baseline testing and randomization into two arms with n=27 per arm. After study attrition, we conservatively expect that 36 individuals will complete 30 hours of TCT and longitudinal (12 week post-TCT) testing, and that attrition will be roughly balanced to arrive completed samples of n=18 per study arm.

Example of CONSORT Diagram of proposed R33 study

\* Conservative estimate of final n=18/arm for Aim 2 analyses

To meet these recruitment and retention needs, men and women with a SZ disorder are recruited from the San Diego community using our long-established network and recruiting procedures, as per. Our full-time patient recruiters have established longstanding relationships with club houses and board-and-care facilities in San Diego County that serve this patient population. Our laboratory participates in events at these facilities (e.g. MHA Visions Clubhouse in Chula Vista recently hosted a “What Wellness Looks Like” Mental Health Awareness and Creative Arts show to celebrate Mental Health Awareness Month), as well as recruitment events (e.g. “NAMI Walks”) hosted by NAMI-San Diego. The PI is a former member of the NAMI-SD Board of Directors and Chair of their Medical Advisory Board, and has maintained strong relationships with this organization that facilitate recruitment. Study advertisements are placed in local newspapers, and on relevant websites, including the PI’s website dedicated to this study. The URL for this site (<http://www.psychiatry.ucsd.edu/research/Pages/psychiatryresearch.aspx>) can be accessed through links entitled “Psychiatry Research” on our Department’s website (<http://www.psychiatry.ucsd.edu/research/Pages/default.aspx>) and on the UCSD CTRI website for “Studies Recruiting Volunteers” (<http://ctrif.ucsd.edu/community/Pages/studies-recruiting-volunteers.aspx>). Our studies are also listed on ResearchMatch, and Clinicaltrials.gov. The lead Co-Investigator, [name], has ongoing funded collaborations with local residential treatment facilities, as described in this application, and patients who do not participate in TCT studies at these facilities are eligible for participation in this application. Other recruitment sources include the UCSD Medical Center Outpatient and Inpatient Psychiatric Services (both of which are staffed by Psychiatry Residents in the UCSD Psychiatry Research Residency Training Program, for which the PI serves as Director), as well as outlying community clinics staffed by UCSD Residents.

Study enrollment is reviewed at weekly diagnostic consensus meetings, and is documented in quarterly milestone reports. There are expected seasonal differences in recruitment patterns, based on University Holidays (e.g. Winter Holidays, during which time no TCT training takes place), and Resident caseload transfers (July, when a "bolus" of referrals can be expected). Nonetheless, any deviation from expected recruitment targets is identified, analyzed and addressed. Primary responsibility to track and retain participants is delegated to [name].

Study retention is enhanced by: 1) transportation provided to and from each laboratory visit; 2) careful attention to participant needs including schedule flexibility; 3) a comfortable laboratory environment, including availability of healthy meals and snacks; 4) reminder phone calls for all post-TCT visits; 5) careful follow-up protocol for all missed visits; 6) subject payment.

Recruitment of subjects and informed consent procedures will follow [name] established methods. For all subjects we will have a consent form describing all laboratory measures and any potential side effects they may expect from AMPH. Specifically, all subjects will be asked to read a description of AMPH, which includes the following information: 1) the typical indications for this drug; 2) the recommended starting dose for this drug, and details regarding typical maintenance doses and schedules; 3) common side effects experienced by individuals taking this drug, based on trials with in SZ patients; and 4) an assessment of the likelihood that they will experience significant side effects from this drug, in the dose to be used in this study. In all cases, fully informed consent will be obtained and a study M.D. will be directly available to clarify any questions raised by a subject. Signed and witnessed consents will be kept on file with other patient data. The UCSD IRB application is under review; in our past protocols for AMPH studies in this population, we have had no waivers or modifications of normal procedures.

Subjects will be carefully screened to ensure their ability to comprehend study procedures, risks, and benefits. Potential participants will be fully informed of all risks and benefits prior to giving their written informed consent and prior to enrollment in the study. Participants will be asked to repeat back understanding of this material, and if there is any question as to whether a person is able to provide informed consent then they will not be permitted to participate. A copy of the signed consent form will be stored in a separate locked filing cabinet from other de-identified coded materials, and a copy will be given to the study participant.

All study personnel involved in obtaining written informed consent will have completed a web-based course with post-test on Human Subject Research Protections and Good Clinical Practice, in addition to being trained by the PI on obtaining informed consent. These study personnel will also be authorized to obtain informed consent by the IRB and Human Studies Subcommittee. Informed consent will be documented using standardized IRB-approved forms. The forms will be presented to all potential participants at the initial visit. Briefly, the informed consent form will describe the purpose of the study, procedures and participant involvement, nature of assessments and treatments, potential risks, alternatives to participation, costs and compensation, confidentiality, right to withdraw, potential benefits, relevant contact personnel, and information regarding the Health Insurance Portability and Accountability Act (HIPAA) of 1996. Because participation in the proposed study is entirely voluntary, patients can choose to discontinue the study at any point for any reason and this will in no way affect future medical treatment decisions or practices.

Payment is \$15/hr. This equates roughly to \$45 for completion of the screening visit, \$45 per visit for each of the 30 TCT sessions, except sessions 10, 20 and 30 (\$75), \$60 for post-week 30 biomarker testing and \$45 for week 22 testing. For the full R33 screening, testing, training and follow-up, subjects are paid a total of \$1590. This payment is required to: 1) maintain subject flow and thereby avoid cost-ineffective "down time"; 2) attract subjects from non-indigent populations, and thereby avoid high rejection rates due to health and drug exclusion criteria and subject.

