**Fig. 8. “Go” criteria: #1, plus at least one of #’s 2, 3 & 4 ( $d > 0.5$ )**

1. **Target engagement:** APS learning, AMPH > PBO,  $p < 0.05$
2. **Greater clinical, neurocognitive or functional gains:**
  - $\downarrow$ PANSSt,  $\uparrow$ MCCB-C or  $\uparrow$ Fnxn: AMPH+TCT > PBO+TCT
3. **Faster clinical, neurocognitive or functional gains:**
  - drug group x session interaction ( $p < 0.05$ ) followed by AMPH+TCT > PBO+TCT at specific session # or combination;
4. **More durable** clinical, neurocognitive or functional gains:
  - AMPH+TCT > PBO+TCT at post-TCT week 12.

PANSSt: Positive & Negative Symptom Scale total; MCCB-C: MATRICS Composite; Fnxn: Function (assessed via the World Health Organization Disability Schedule 2.0 (WHODAS))

**Outcome and “Go Decisions”.** In addition to confirming “target engagement”, this application tests the hypothesis that SZ patients given AMPH +TCT will exhibit greater, faster and/or more durable improvements (change from baseline) in symptoms, neurocognition and/or function compared to patients given PBO+TCT, and that this enhanced clinical response will be associated with greater AMPH-enhanced TCT learning.

The small “n” necessitated by the 3-year timeline and demanding treatment schedule greatly constrains the total number of outcome measures.

Moreover, the plan to assess not only magnitude but also rate and durability of PACT gains triples the number of primary analyses. Thus, we selected only one **primary** clinical, neurocognitive and functional outcome measure (Fig. 8) – recognizing that they are relatively “blunt” metrics - but will track several other, more focused, measures as well as inter-measure correlations in exploratory analyses to inform future studies.

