A “Go” decision requires: 1) confirmation of target engagement (APS learning, AMPH>PBO,  $p < 0.05$ ); 2) evidence of gains from PACT ( $d \geq 0.5$  (AMPH > PBO)) in primary clinical, neurocognitive and/or functional measures (Fig. 8), and 3) the absence of adverse effects of AMPH that are significantly greater than PBO levels. The decision to not use traditional statistical significance as “Go” criteria for Aim 2 reflects this RFA’s call for “Pilot” studies, the need to identify candidate treatments for a subsequent larger “n” Confirmatory Efficacy R01 study, and the limits in sample size resulting from the 3-year R33 duration. Cohen defined a medium effect size ( $d=0.5$ ) as one that is “visible to the naked eye,” and this amount of change is viewed as clinically meaningful in trials targeting negative symptoms. This  $d=0.5$  “Go” threshold for Aim 2 corresponds to a “number needed to treat” (NNT) value  $\approx 3.62$ . While a “Go” decision does not require identification of a biomarker predicting greater PACT

sensitivity (Aim 3), the identification of one or more meaningful predictors that could be incorporated into a Confirmatory Efficacy trial would favorably impact a “Go” decision.

Staff assessing outcome measures are blind to treatment arm, and for some measures receive training using videotaped and practice interviews until achieving high (ICC>.80) reliability based on 20 assessments by 2 raters. We achieve high inter-rater reliability (e.g., ICC>0.85 for PANSS total), and check for rater drift each 90d.

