**Aim 2 – Test clinical, neurocognitive and functional impact of AMPH on TCT, and its relationship to target engagement:** We will determine if AMPH+TCT produces greater, faster or more durable clinical, neurocognitive or functional gains from baseline, compared to PBO+TCT, over a 30-session course of TCT. A Cohen’s  $d \geq 0.5$  for the main effect of drug (PBO vs. AMPH) or drug x session (#10, 20, 30) interaction in an LME model is the primary “Go” criteria. The main effect of drug assesses “greater” gains. Reverse Helmert contrasts for session assesses “faster” gains. A separate model comparing differences in outcomes at 12-weeks post-TCT assesses “more durable” gains. Secondary regression analyses will examine whether change in AMPH-enhanced APS learning (“within-subject” target engagement; Aim 1) predicts gains in Aim 2 outcome measures.

**Aim 3 – Biomarkers of AMPH-induced gains:** We will determine if baseline levels of specific neurocognitive or EEG-based measures, or changes in specific measures with initial AMPH exposure (Test 2 vs. 1), predict greater sensitivity to AMPH-enhanced neurocognitive, clinical or functional gains over 30-h of TCT. Regression analyses will assess whether specific candidate biomarkers predict AMPH-enhanced gains in outcome measures.

**Subject “throughput”:** We will enroll and screen 23 subjects/yr, test target engagement in 18 subjects/yr, and (conservatively) complete TCT training in 12 subjects/yr. This will yield 2 “target engagement” Aim 1 arms of  $n=27$ , and (conservatively) 2 TCT completion Aim 2 arms of  $n=18$ . Training capacity (2 TCT stations with morning and afternoon sessions on M, W and F, with T and Th “make-up” days for missed appointments, 48 weeks/year) allows for a “maximum throughput” of 19.2 subjects/yr. To reach the target of **12 TCT-completing subjects /year**, we would need to maintain training rates of **62.5% capacity**. This is well within our historical testing levels.

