3. Evaluating the quality of the ongoing study conduct by performing quarterly evaluations of the study accrual, compliance with eligibility, participant adherence to study requirements, and accuracy and completeness of data;
4. Considering factors external to the study when relevant information becomes available, such as scientific or therapeutic developments that may have an impact on the safety of the participants or the ethics of the study;
5. Recommending appropriate study review or temporary halting for any SAE, and termination due to the occurrence of 3 SAEs (symptom exacerbation or suicidality associated specifically with active treatment vs. PBO), or inability of PI to provide necessary assessment information or to answer study questions;
6. Recommending continuation of ongoing studies at quarterly reviews;
7. Considering the overall picture, including need to pursue both primary and appropriate secondary analysis, and making these recommendations during the final months of PY3 (see “Timeline”);
8. Consider modifying sample sizes based on unexpectedly robust therapeutic benefits; and
9. Reviewing final results, via DSMB report by PI within 90 days of completion of final R33 subject.

**The DSMP** proposes both the “process” and “content” of the DSMB, including its deliberative processes, event triggers that would call for an unscheduled review, stopping guidelines, unmasking (unblinding) and voting procedures prior to initiating any data review. Elements of the DSMP include:

1. How risks are minimized (e.g. see “Protection of Human Subjects” section on inclusion and exclusion criteria, careful clinical monitoring including specific scales for suicidality and psychosis and specific criteria for interventions based on these scales);
2. How risks are reasonable in relation to anticipated benefits (see “Protection of Human Subjects” re: risk/benefit ratio);
3. Plan to monitor progress and safety (see below for description of adverse events and related protocol);
4. Assessments of data quality, timeliness, participant recruitment, accrual and retention;
5. Plan to assure compliance with reporting of adverse events and/or unanticipated problems involving risk to participants or others (see below for details):

- a. Process for detecting and reporting serious and unexpected adverse events and/or unanticipated problems involving risk to participants or others;
- b. Who will be monitoring and collecting the adverse events;

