Primary	MATRICS Consensus Cognitive Battery Global Composite T-score (MCCB-C)	baseline vs. post-TCT session 10, 20 and 30 (approximately 10 weeks), and 12 weeks post-TCT	The MCCB measures 7 separable cognitive domains. Details are found in cited reports including past studies by the PI of drug effects on MCCB performance. Since the MCCB is assessed multiple times, alternate forms of the HVLT-R and BVMT-R are administered in counterbalanced order. MCCB Global Composite T-score (MCCB-C) is the primary neurocognitive outcome measure. Individual MCCB domain T-scores are used in secondary analyses to determine whether an overall effect is driven by specific aspects of neurocognition; specifically, TCT effects on verbal learning performance are known to be robust, and should be augmented by AMPH. Baseline MCCB performance (attention/vigilance subscale) will also be tested as a potential biomarker/ moderator of AMPH efficacy.
Primary	World Health Organization Disability Schedule (WHODAS 2.0)	baseline vs. post-TCT session 10, 20 and 30 (approximately 10 weeks), and 12 weeks post-TCT	Function will be assessed via the World Health Organization Disability Schedule 2.0 (WHODAS 2.0) at baseline, after sessions 10, 20 and 30, and week 12 post-TCT. WHODAS 2.0 is a 12-item patient-rated measure (< 15 min) using a 5-point Likert scale focusing on 6 domains: cognition, mobility, self-care, getting along with people, life activities, participating in society; it was recommended by the DSM-5 Task Force committee to replace the global assessment of functioning (GAF) scale.

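### The 36 patients expected to have 12-week post-TCT data equal three full years of the stated rates, with no time left for follow-up; on the plan's own figures a 3-year award yields about 30 to 33

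*Protocol*

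**What the plan says.** The Recruitment and Retention Plan gives the overall flow: "we will consent 69 SZ individuals for screening, from whom we will advance 54 individuals to in-laboratory baseline testing and randomization". After attrition, "we conservatively expect that 36 individuals will complete 30 hours of TCT and longitudinal (12 week post-TCT) testing", balanced at 18 per arm. The Subject throughput paragraph under Data Analysis gives the rates: "We will enroll and screen 23 subjects/yr, test target engagement in 18 subjects/yr, and (conservatively) complete TCT training in 12 subjects/yr". There the same 18 per arm is the number completing TCT, with no mention of the later visit.

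The duration is given twice in the paragraphs on outcome and Go decisions. The small sample is "necessitated by the 3-year timeline and demanding treatment schedule", and the Aim 2 criterion reflects "the limits in sample size resulting from the 3-year R33 duration". Protection of Human Subjects explains the fall from 69 to 36 by screen failure and attrition only.

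For all three Aim 2 primary outcomes, Synopsis 4.3 sets the time frame as "baseline vs. post-TCT session 10, 20 and 30 (approximately 10 weeks), and 12 weeks post-TCT". Week 12 is also a separate route to Go: criterion 4 in Fig. 8, with its own model under Aim 2.

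**The concern.** Each planned total is its yearly rate times exactly three, so entry, TCT completion and the week-12 visit all appear to run at full rate over the same 36 months. A patient needs 5 to 7 days between Tests 1 and 2, about 10 to 12 weeks of TCT and 12 weeks of follow-up to reach the last primary time point. Patients who enter late in year 3 cannot get there by month 36.

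The durability route to Go compares an observed d with 0.5 and, as the Aim 2 text describes it, does not require significance. The number of patients at week 12 therefore directly sets how often chance alone crosses the threshold. If that number is smaller than stated, the evidence behind a durability Go is weaker than the plan implies.

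**Working it through.** **Inputs.** Rates of 23, 18 and 12 per year and capacity of 19.2 per year (Subject throughput). Totals of 69, 54 and 36 (Recruitment and Retention Plan). Duration of 3 years, or about 156.5 weeks (outcome and Go decisions). Test 1 to Test 2, 5 to 7 days; TCT, 10 to 12 weeks (Synopsis 4.2.a), with a 65-day mean in the team's experience (Assessments); follow-up, 12 weeks (Synopsis 4.3).

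**1. The plan's own figures.** 23 × 3 = 69, 18 × 3 = 54 and 12 × 3 = 36. Capacity is 4 slots × 48 weeks / 10 weeks = 19.2 per year, and 12 / 19.2 = 62.5%. All match the protocol.

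**2. Time from Test 1 to week 12.** With the 65-day mean: 6/7 + 65/7 + 12 = 22.1 weeks. With the longest stated values: 1 + 12 + 12 = 25 weeks. The protocol's own label for the last visit is week 22. The range is 22 to 25 weeks.

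**3. Rates read as entry-based.** Under even entry over 156.5 weeks, the share not reaching week 12 by month 36 is lag / 156.5:
- 22 / 156.5 = 14.1%, leaving 36 × 0.859 = 30.9
- 25 / 156.5 = 16.0%, leaving 36 × 0.840 = 30.3

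At the stated rates all 36 would have week-12 data only at about month 41 to 42 (36 months plus 22 to 25 weeks).

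**4. The 12 per year read as TCT completions from month 0.** Only the 12-week tail is lost: 12 / 156.5 = 7.7%, and 36 − 12 × 12 / 52.18 = 33.2. This is a generous reading, because the first patient cannot finish 30 sessions until about 10 weeks after starting.

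**5. What 36 would need on the entry-based reading.** Entry must end 22 to 25 weeks before month 36, which leaves 2.58 to 2.52 years:
- consented: 69 / 2.58 to 69 / 2.52, about 27 per year
- randomised: 54 / 2.58 to 54 / 2.52, about 21 per year
- completers: 36 / 2.58 to 36 / 2.52, about 14 per year, or 73% to 74% of 19.2

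**6. Effect on the week-12 contrast under 1:1 allocation.** The 95% half-width at d = 0.5 is 1.96 × √(2/n + d²/(4n)), with n per arm. The chance of an observed d of at least 0.5 with no true effect is P(Z > 0.5 / √(2/n)).

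| n per arm | half-width | chance with no effect |
|---|---|---|
| 18 | 0.66 | 6.7% |
| 16.6 (33.2 in total) | 0.69 | 7.5% |
| 15 (30 in total) | 0.73 | 8.5% |

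These chances are for one outcome at one time point. They are not the overall chance of a Go, which also requires target engagement at p < 0.05.

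**The case against.** The strongest reply is that no supplied text promises 36 by month 36. The Recruitment and Retention Plan speaks of the course of the study, and the other sections say only that the award length limits the sample. DSMB item 7 cites a Timeline, which is not in the supplied text and may show when entry closes or whether follow-up runs past the award. This stands, so even accrual and a stop at month 36 are assumptions here.

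It also stands that the figures have slack. The protocol calls 36 conservative and the enrolment rate approximate, and 12 per year uses only 62.5% of capacity. On the entry-based reading about 45 to 46 of the 54 randomised would have enough time, so 78% to 79% completion, against the planned 36 / 54 = 67%, would still give 36. But the plan states neither that retention nor the faster rates.

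A reader might infer that the DSMB list contradicts itself, since item 7 covers the analyses, "including need to pursue both primary and appropriate secondary analysis, and making these recommendations during the final months of PY3", while item 9 provides for review of final results "via DSMB report by PI within 90 days of completion of final R33 subject". The documents do not support that. Item 7 concerns which analyses to pursue and item 9 the review of results, and the two can follow in order. Nor does any passage place the Go decision in the final months of year 3, so a larger shortfall dated to that point would be conjecture.

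Finally, the SAP's Project Modification section has overtaken the target. It reports lagging recruitment, pooled placebo groups and 2:1 allocation, and its effect sizes run from baseline to the post-session-30 assessment. It gives no new week-12 number. In the SAP's earlier durability analysis, which uses data from the end of TCT to week 12, patients without the last visit would still contribute some information.

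**Conclusion.** The concern holds as a mismatch between a stated size and the plan's own rates and duration. The protocol attaches 36 to TCT completion in one place and to TCT plus the 12-week visit in another, and three years at the stated rates does not deliver the second on either reading. The expected number is about 30 to 31 if the rates follow entry (14% to 16% short) or about 33 if 12 per year is a completion rate (8% short). Both rest on even accrual from month 0, data collection ending at month 36 and attrition as stated. Start-up or screening time would lower them further: an assumed 2-week screen added to the longest lag gives 36 × (1 − 27/156.5) = 29.8.

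A reader might take 30, or 15 per arm, as the settled figure. The documents do not support that, given the wording of the completion rate, the missing Timeline and the later 2:1 allocation. The loss of precision is small and touches one of three clinical routes to Go in a pilot. It is worth correcting because that route depends on an effect-size threshold.

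**What to change.** In the Subject throughput paragraph, the Recruitment and Retention Plan and Protection of Human Subjects, do one of two things:
- Restate the number expected to have 12-week post-TCT data within the award as about 30 to 33 in total. Do not give it per arm, because allocation later became 2:1.
- Keep 36 and restate what it needs: about 27 consented, 21 randomised and 14 completers per year, with the 62.5% capacity figure changed to about 73% to 74%.

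Also state that any week-12 durability contrast, and a Go decision that uses it, is run after the last randomised patient's 12-week post-TCT visit. This agrees with DSMB item 9. If the Timeline already shows entry closing early or follow-up beyond the award, a cross-reference to it with the matching rates would be enough.

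The cost is wording only: a slightly less favourable number, more demanding stated rates, or a final analysis dated about 22 to 25 weeks after the last patient's Test 1. No patients or procedures are added.
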